### Prior therapy

An overview of prior therapies for Breast carcinoma will be provided giving:

- Number of patients with at least one prior therapy
- Number of patients treated by medication
  - Number of patients treated by chemotherapy
  - Number of patients treated by hormonotherapy
  - Number of patients treated by other antineoplastic drug
- Number of patients who underwent a surgery
- Number of patients who underwent a radiotherapy
- For the last Medication (including chemotherapy, hormone therapy, antineoplastic therapy): intent, time between stop date of medication and date of relapse/progression (expressed in weeks).
- For surgeries: number of surgeries
- For the last radiotherapy: intent

### *Chemotherapy*

- Number of patients who underwent a chemotherapy with intents and intent of last chemotherapy,
- Number of lines,
- Prior anthracycline-based chemotherapy by intent,
- Categorized group of prior cumulative dose of anthracyclines, by type of anthracyclines:
  - No Anthracyclines,
  - Epirubicin  $\geq 300$  mg/m^2,
  - Epirubicin  $< 300$  mg/m^2,
  - Epirubicin dose unknown,
  - Doxorubicin/Pirarubicin  $\geq 180$  mg/m^2,
  - Doxorubicin/Pirarubicin  $< 180$  mg/m^2,
  - Doxorubicin/Pirarubicin dose unknown,
  - Epirubicin  $\geq 300$  mg/m^2 / Doxorubicin/Pirarubicin  $\geq 180$  mg/m^2,
  - Other (Liposomal Doxorubicin).
- Prior taxane-based chemotherapy by intent,
- Categorized group of prior taxanes:
  - Docetaxel at any dose,
  - Paclitaxel at any dose.
- Class of prior adjuvant/neo-adjuvant chemotherapy (if both in the same time):
  - anthracyclines-based,
    - anthracyclines-taxanes
    - anthracyclines-other
    - anthracyclines single agent
  - taxanes-based,
    - taxanes-anthracyclines,
    - taxanes-other,
    - taxanes single agent, ...

- Class of prior advanced disease chemotherapy: anthracyclines-based, anthracyclines-taxanes, anthracyclines-other, anthracyclines single agent, taxanes-based, taxanes-anthracyclines, taxanes-other, taxanes single agent
- Best response of the last chemotherapy by intent and by class of chemotherapy,
- Best response of the last chemotherapy by HER status (0/1+/2+/3+/missing/not done)

#### *Hormone therapy*

- Number of patients who underwent a hormone therapy with intents and intent of last hormone therapy,
- Details of hormone therapy treatments received.
- Number of patients who underwent a castration,

#### Clinical examination

- Electrocardiogram (normal/abnormal but not clinically significant/abnormal clinically significant),
- Temperature, Blood Pressure, Pulse,
- Baseline biological abnormalities,
- Baseline haematological abnormalities.

Last available baseline value will be used for baseline analysis.

#### Concomitant medications at baseline

- Concomitant medications whatever the intent,
- Concomitant medications with a tumour related intent,
- Concomitant medications with a prophylactic intent,
- Concomitant medications with pre-treatment event indication,
- Concomitant medications with a medical history,

#### Prior medical history

- Prior medical or surgical history according to MedDRA Preferred Term (PT) and System Organ Classification-(SOC).

#### Pre-treatment events

- Pre-treatment events according to MedDRA Preferred Term (PT) and System Organ Classification (SOC),

## **9.2. DESCRIPTION DURING THE STUDY**

In arm A, a cycle is defined as 1 administration of vinflunine (day 1) and 14 consecutive days (starting from day 1) of capecitabine doses bi-daily with treatment rescheduled every 3 weeks.

In arm B, a cycle is defined as 14 consecutive days of capecitabine doses bi-daily, with treatment rescheduled every 3 weeks.

Duration of exposure is defined as the time elapsed between the date of 1st intake and the date of last capecitabine (if given) administration + 7 days or day 1 (administration of vinflunine) + 21 days if capecitabine not given.

A summary table will provide by treatment arm, the following items:

- Duration of exposure,
- Number of patient with at least one dose permanently discontinued,
- Number of patient with at least one dose temporarily cancelled,
- Number of patients with at least one dose reduced (including dose delayed and reduced),
- Number of patients with at least one dose delayed (including dose delayed and reduced).

The total number of cycles given during the study, the median number of cycles as well as the number of patients by cycle will be given. The categorized groups of vinflunine and capecitabine doses by cycle will be presented.

The actual dose (mg/m^2) will be calculated from the total dose administered (mg) divided by the BSA. The BSA will be recalculated at each cycle.

The following categories of vinflunine and capecitabine doses will be used:

**Table 9-1 : Categorized dose of vinflunine**

Dose category in mg/m 	Dose of vinflunine in mg/m 
>320	] 335 - ∞]
320	] 300 – 335 ]
280	] 265 - 300 ]
250	] 237.5 - 265 ]
225	] 212.5- 237.5 ]
< 225	] 0 - 212.5 ]

**Table 9-2: Categorized bi-daily dose of capecitabine**

Dose category in mg/m 	Dose of capecitabine in mg/m 
Arm A	
> 1250	]1400 – ∞[
1250	]1100–1400]
950	]887.5–1100]
825	] 742.5–887.5]
660	]642.5–742.5]
625	]562.5–642.5]
500	] 437.5–562.5]
<500	] 0–437.5]
Arm B	
> 1250	]1400 – ∞[
1250	] 1100-1400]
950	] 787.5–1100]
625	] 462.5–787.5]
<625	] 0–462.5]

Actual dose intensity (mg/m^2/wk) and relative dose intensity (%) will be calculated per cycle and per patient for the vinflunine plus capecitabine and the capecitabine alone arms. Cumulative dose (mg/m^2) will also be given. Descriptive statistics such as median and range will be provided.

The number and percentage of cycles/patients with a RDI ≤ 90%, in ]90%;100%] or > 100% will also be given.

The actual dose received (mg/m^2) at cycle *i* will be equal to the actual dose received (mg) at cycle *i* divided by the body surface area at the beginning of the cycle *i*.

The body surface area will be calculated as follows:

$$BSA = \frac{(W^{**}0.425 \times H^{**}0.725 \times 71.84)}{10000}$$

where:

- W = Weight (kg) at the beginning of cycle *i*, or last weight available if missing at cycle *i*,
- H = Height (cm) at the beginning of the study.

BSA as per investigator will be used as an estimate when height has not been provided at baseline.

### 9.2.1. Actual Dose intensity per cycle

Actual dose intensity per cycle will be defined as follows:

$$DI \text{ at cycle } i = \frac{\text{Actual dose received (mg/m}^2\text{) at cycle } i}{\text{Actual duration of cycle } i \text{ (wk)}} = \frac{\text{Actual dose received (mg/m}^2\text{) at cycle } i}{[(\text{Course date at cycle } i + 1) - (\text{Course date at cycle } i)]/7}$$

The duration of the last cycle will be estimated to be 3 weeks.

### 9.2.2. Relative dose intensity per cycle

Relative dose intensity (%) at cycle n° *i* will be the ratio of the actual dose intensity (mg/m^2/wk) at cycle *i* to the planned dose intensity (mg/m^2/wk) that is to say:

$$RDI \text{ at cycle } i = \left( \frac{DI \text{ at cycle } i}{PDI} \right) \times 100 = \left( \frac{\text{Actual dose intensity at cycle } i \text{ (mg/m}^2\text{/wk)}}{\text{Planned dose intensity (mg/m}^2\text{/wk)}} \right) \times 100$$

where :

$$PDI \text{ at cycle } i = \frac{\text{Planned dose (mg/m}^2\text{)}}{\text{Theoretical duration of cycle } i \text{ (wk)}} = \frac{\text{Planned dose (mg/m}^2\text{)}}{3}$$

Tables 9-3 and 9-4 give for each treatment arm of the study the PDI :

**Table 9-3: Planned dose intensity in mg/m^2/wk in the vinflunine plus capecitabine arm**

Treatment	Administration	Dose (mg/m  )	Planned Dose (mg/m  ) per cycle	P.D.I (mg/m  /wk)
vinflunine	Day 1	280	280	93.33
capecitabine	Bid from day 1 to 14	825	23100	7700

**Table 9-4: Planned dose intensity in mg/m^2/wk in the capecitabine arm**

Treatment	Administration	Dose (mg/m  )	Planned Dose (mg/m  ) per cycle	P.D.I (mg/m  /wk)
capecitabine	Bid from day 1 to 14	1250	35000	11666.67

### 9.2.3. Actual Dose intensity per patient

Actual dose intensity per patient will be defined as follows :

$$DI = \frac{\text{Cumulative dose (mg/m}^2\text{)}}{\text{Treatment duration (wk)}} = \frac{\sum_{i=1}^n \text{dose}_i}{\sum_{i=1}^n \text{duration}_i}$$

where :

- dosei = actual dose received (mg/m^2) at cycle *i*,
- durationi = actual duration (wks) of cycle *i*,
- n = total number of cycle(s) per patient.

### 9.2.4. Relative dose intensity per patient

Relative dose intensity (%) will be the ratio of the actual dose intensity (mg/m^2/wk) to the planned dose intensity (mg/m^2/wk) that is to say :

$$RDI = \left( \frac{DI}{PDI} \right) \times 100 = \left( \frac{\text{Actual dose intensity (mg/m}^2\text{/wk)}}{\text{Planned dose intensity (mg/m}^2\text{/wk)}} \right) \times 100$$

where :

$$PDI = \frac{\text{Planned dose (mg/m}^2\text{)} \times \text{number of cycles}}{\text{Theoretical duration of a cycle (wk)} \times \text{number of cycles}} = \frac{\text{Planned dose (mg/m}^2\text{)}}{3}$$

### 9.2.5. Dose reductions

Dose reductions are allowed by the study protocol for vinflunine and capecitabine in both arms. The number of patients and cycles with a dose reduction will be presented as well as the reasons.

#### 9.2.5.1. Vinflunine dose reduction at day 1 (Arm A)

- Number of patients with at least one dose of vinflunine in arm A reduced at day 1
- Number of cycles with a dose of vinflunine in arm A reduced at day 1
- Reasons for vinflunine dose reduction at day 1 (as per protocol):

Reason for dose reduction of vinflunine	Dose reduction as per protocol				N cycles	
	From 280 to 250 mg/m 		From 250 to 225 mg/m 			
	N	%	N	%	N	%
Non-study drug related adverse event						
Study drug related haematological AE						
Study drug related non-haematological AE						
Other						

- Total number of haematological and non-haematological toxicities and nature, as per protocol or not, which have led to a dose reduction,
- Detail of the haematological and non-haematological toxicities which have led to a dose reduction,

#### 9.2.5.2. Capecitabine dose reductions

- Number of patients with at least one dose of capecitabine reduced:
- Number of cycles with at least dose of capecitabine reduced:
- Reasons for capecitabine dose reductions (as per protocol)
- Total number of haematological and non-haematological toxicities, which have led to a dose reduction of capecitabine,
- Detail of the haematological and non-haematological toxicities which have led to a dose reduction of capecitabine,

### 9.2.6. Treatment cancellation (Capecitabine)

Capecitabine dosing may be cancelled as per protocol (§ 5.4.3.2 of the protocol).

The number of cycles with at least one day (morning and afternoon doses both not taken for capecitabine) cancelled and number of patients with at least one day of dosing cancelled will also be displayed. Reasons for treatment cancellation will be provided.

- Number of patients with at least one capecitabine dose cancelled,
- Number of cycles with at least one capecitabine dose cancelled,
- Reasons for capecitabine dose cancellation.
- Total number of toxicities, as per protocol or not, which have led to a capecitabine dose cancellation,
- Detail of the haematological and non-haematological toxicities which have led to a capecitabine dose cancellation,

### **9.2.7. Vinflunine infusion interruption (Arm A)**

Vinflunine infusion interruption may occur. The number of patients and cycles with a infusion interruption will be presented as well as the reasons.

- Number of patients with at least infusion of vinflunine in arm A interrupted at day 1,
- Number of cycles with a infusion of vinflunine in arm A interrupted at day 1,
- Reasons for vinflunine infusion interruption at day 1,
- Total number of toxicities, as per protocol or not, which have led to a infusion interruption,
- Detail of the haematological and non-haematological toxicities which have led to a infusion interruption,

### **9.2.8. Treatment delay**

The number of patients and cycles delayed will be presented with reason for treatment delay.

A treatment cycle will be considered as delayed if administered  $\geq 4$  days after the planned date with a three weeks interval from day 1 of previous cycle. In arm A, the date of vinflunine administration will determine the day 1 of the cycle; in arm B (and for patients continuing capecitabine alone in arm A), the first day of capecitabine intake will determine the day 1 of the cycle, whatever the first dose has been taken in the morning or the afternoon. Only delay for Day 1 will be calculated.

The delays will be categorized as follows:

- [4 – 7 days[,
- [7 – 14 days[,
- $\geq 14$  days.

The following parameters will be described by arm:

- Number of patients with at least one cycle delayed by four days or more,
- Number of cycles delayed,
- Categorized groups of cycle delay,

- Reasons for cycle delay of four days or more,
- Total number of haematological and non-haematological toxicities, and nature, as per protocol or not, which have led to a dose delay,
- Detail of the haematological and non-haematological toxicities which have led to a delay,

### 9.2.9. Route of administration and setting

The route of vinflunine administration and setting in arm A will be presented by patient and by cycle.

- Route of administration and setting by patient and by treatment arm:

	Arm A	
	N	%
Route of administration Central venous line Peripheral vein		
Change in route of administration No Yes		
Setting Out-patient clinic In-patient clinic		
Change in setting No Yes		
Number of patients		

- Route of administration by cycle:

Courses	Arm A	
	Central venous line N (%)	Peripheral vein N (%)
1		
2		
3		
4		
5		
6		
...		
Number of cycles		

### 9.2.10. Concomitant medications

Medications administered concomitantly with the study treatment will be summarized according to the prophylactic indication, tumour related indication, pre-treatment events or medical history indication and whatever the indication, by patient and by cycle.

## **10. EFFICACY ANALYSES**

### **10.1. PRIMARY EFFICACY ANALYSIS**

The primary efficacy population will be the intent-to-treat (ITT) population.

As the final population size is much lower than the population size required to ensure adequate statistical power, no statistical test will be performed.

PFS will be described by treatment arm. Hazard ratio and 95% confidence interval of the hazard ratio will be computed using the SAS® procedure «PHREG». The treatment arm will be entered as a covariate in the Cox proportional hazard model and the variables of stratification at randomisation (except centre) will be entered as stratification factors in the model. Kaplan-Meier curves will also be provided by treatment arm.

### **10.2. SENSITIVITY ANALYSES OF THE PRIMARY EFFICACY PARAMETER**

No sensitivity analyses of the primary efficacy parameter will be performed.

### **10.3. SECONDARY EFFICACY ANALYSES**

Not Applicable.

## **11. SAFETY ANALYSES**

Safety analysis will be performed on the evaluable population for safety described in section 7.4 for each treatment arm.

### **11.1. OVERVIEW OF THE SAFETY**

The adverse events incidence, overall and per CTCAE grade, will be presented. The worst CTCAE grades or maximum severity grades (for non haematological adverse events not classified by the CTCAE) will be analysed by cycle and by patient, and by treatment arm, regardless or not to the relationship to treatment.

For definition of evaluable cycle/patient for non-haematological and haematological toxicity, see § 5.1 and § 5.3, respectively.

Some laboratory toxicities will be presented when reported as adverse events according to the study completion guidelines.

Listings of adverse events not graded and those one occurring during follow up will be provided. The pre-treatment events will also be presented.

## **11.2. ADVERSE EVENTS**

### **11.2.1. All adverse events**

The incidences of the treatment-emergent adverse events (TEAE) as defined in 5.1, graded according to NCI-CTCAE version 3.0 will be presented using the MedDRA SOC and PT defined during the MedDRA coding process.

A summary table will provide by treatment arm the following:

- On treatment deaths
- Patients with at least one AE
- Patients with at least one TEAE (overall and by grade)
- Patients with at least on SAE
- Patients with at least one TEAE leading to discontinuation
- Patients with at least one TEAE requiring dose interruption and/or adjustment
  - Patients with at least one TEAE requiring dose interruption
  - Patients with at least one TEAE requiring dose adjustment
- Patients with at least one TEAE requiring additional therapy
- Cycles with at least one AE
- Cycles with at least one TEAE (overall and by grade)

Overall incidences per patient and per cycle will be depicted as well as the incidence of non related and related toxicities only. An analysis will also present the CTCAE grade presented for each SOC and PT per patient and cycle according to the relationship with study treatment.

### **11.2.2. Serious adverse events**

The number of patients with at least one SAE, one related (suspected and insufficiently documented) SAE, number of SAEs, number of related SAEs will be tabulated. Incidences of SAEs by SOC and PT will be presented according to the relationship with study treatment.

A listing of the serious adverse events will be also provided with the following variables: patient number, cycle number, seriousness, CTCAE grade, date of onset, date ceased, action taken with study drug, corrective treatment and causality

### **11.2.3. Deaths**

The number and percent of patients dead will be tabulated by treatment arm, including number and percent of dead related to AE/SAE, due to progression or other reasons.

A listing of the deaths within 30 days after last administration or more than 30 days after last administration will be provided with the following variables: patient number, cycle number, date of death, reason of death, source of information.

## **11.3. LABORATORY TESTS**

### **11.3.1. Haematological toxicities**

Leukocytes, ANC, haemoglobin and platelets data will be analysed for haematological toxicity.

A first analysis will present the worst grade (overall / grade 3/4) by patient and the worst grade (overall / grade 3/4) experienced during a cycle. In a second analysis, the worst grade of patients according to the grade at baseline will be tabulated.

### **11.3.2. Biochemical toxicities**

Liver, renal and metabolic function tests will be analysed with a focus on bilirubin, alkaline phosphatase, SGOT/AST and SGPT/ALT, creatinine, creatinine clearance, sodium, potassium and calcium.

In order to examine the evolution of biochemical toxicities, worst CTCAE grade (hypo and hyper for metabolic function tests) will be analysed in relation to the grade presented by the patient at baseline.

In addition, the relationship between liver involvement at baseline and the worst CTCAE grade during study will be studied for SGOT/AST, SGPT/ALT and bilirubin. The same analysis will be done for the worst CTCAE grade of alkaline phosphatase and liver and/or bone metastases at baseline.

A listing of patients having at least one LDH>IU/L, giving treatment arm, all LDH values and the visceral status at randomisation will be provided.

## **12. CHANGES INTERFERED SINCE LAST VERSION**

According to the protocol amendment PA06 (29/07/2016), the statistical analysis was reduced to:

- Efficacy: a descriptive summary of the primary efficacy variable (PFS) on the ITT population (i.e. no analysis on secondary criteria),
- Safety: a description of safety parameters.

As a consequence, the following analyses have been deleted:

- Adverse events of special interest and specific analysis of constipation, because exhaustive tables of AE will be produced,
- Description over time of values and changes from baseline for laboratory data, because CTCAE grades will be provided,
- Some detailed tables of disease history, prior therapies and concomitant medications, limiting the analyses to an overview of the safety and patients characteristics.

Summary tables of adverse events, prior therapies for breast carcinoma and exposure have been added. Analyses of laboratory values have been specified, such as LBH or Creatinine Clearance.

All data will be provided in individual data listings in appendix 16.2 of the Clinical Study Report.

□

## **LIST OF APPENDICES**

**Appendix 1 : LIST OF TABLES, FIGURES AND LISTINGS**

**Appendix 2 : STATISTICAL ANALYSIS CONVENTIONS**

## 14. APPENDIX 1: LIST OF TABLES, FIGURES AND LISTINGS

SECTION	Title	RTF reference
10.1	Number of Patients enrolled, randomized and treated [All patients]	10_1a.RTF
10.1	Patient disposition [ITT]	10_1b.RTF
11.2	Demographic data [ITT]	11_2_1.RTF
11.2	Statification factors [ITT]	11_2_2.RTF
11.2	Disease History[ITT]	11_2_3.RTF
11.2	Triple negative versus HR positive [ITT]	11_2_4.RTF
11.2	HER-2 negative versus HR [ITT]	11_2_5.RTF
11.2	Summary of Prior therapies for Breast Carinoma [ITT]	11_2_6.RTF
11.2	Prior therapies: chemotherapy [ITT]	11_2_7.RTF
11.2	Prior therapies: hormone therapy [ITT]	11_2_8.RTF
11.2	Clinical examinations at baseline [ITT]	11_2_9.RTF
11.2	Haematological CTCAE grades at study entry [ITT]	11_2_10.RTF
11.2	Biochemical CTCAE grades at study entry [ITT]	11_2_11.RTF
11.4.1.1	Progression-Free Survival (months) [ITT]	11_4_1_1.RTF
11.4.1.1	Progression-Free Survival (months) [ITT]	11_4_1_1_FIG.RTF
12.1	Summary of exposure [ITT]	12_1_1.RTF
12.1	Route of administration and settings by patient [ITT]	12_1_2.RTF
12.1	Route of administration and settings by cycle [ITT]	12_1_3.RTF
12.1	Exposure: Description of cycles [ITT]	12_1_2.RTF
12.1	Exposure: Cumulative dose, actual dose intensity and relative dose intensity by patient [ITT]	12_1_3.RTF
12.1	Exposure: Cumulative dose, actual dose intensity and relative dose intensity by cycle [ITT]	12_1_4.RTF
12.1	Dose delayed and reasons [ITT]	12_1_5.RTF
12.1	Dose reduction of Vinflunine and reasons [ITT]	12_1_6a.RTF
12.1	Reasons by dose reduction of vinflunine [ITT]	12_1_6b.RTF
12.1	Dose reduction of Capecitabine and reasons [ITT]	12_1_6c.RTF
12.1	Reasons by dose reduction of Capecitabine [ITT]	12_1_6d.RTF
12.1	Capecitabine cancellation and reasons [ITT]	12_1_7.RTF
12.1	Vinflunine infusion interruption and reasons [ITT]	12_1_8.RTF
12.2.1	Summary of Adverse Events [Safety set]	12_2_1.RTF
12.2.2	Adverse events whatever their relationship to study drug – Worst grade events per patient by SOC and PT [Safety set]	12_2_2_1a.RTF
12.2.2	Adverse events whatever their relationship to study drug – Worst grade events per cycle by SOC and PT [Safety set]	12_2_2_1b.RTF
12.2.2	Drug-related adverse events – Worst grade events per patient by SOC and PT [Safety set]	12_2_2_2a.RTF
12.2.2	Drug-related adverse events – Worst grade events per cycle by SOC and PT [Safety set]	12_2_2_2b.RTF
12.2.2	Serious adverse events whatever their relationship to study drug – Worst grade events per patient by SOC and PT [Safety set]	12_2_2_3a.RTF
12.2.2	Drug-related Serious adverse events – Worst grade events per patient by SOC and PT [Safety set]	12_2_2_3b.RTF
12.2.2.4	Worst CTCAE grade of haematological parameters by patient [Safety set]	12_2_2_4_1a.RTF

SECTION	Title	RTF reference
12.2.2.4	Worst CTCAE grade of haematological parameters by cycle [Safety set]	12_2_2_4_1b.RTF
12.2.2.4	Shift table of Worst CTCAE grade by patient according to grade at baseline for haematological parameters [Safety set]	12_2_2_4_1c.RTF
12.2.2.4	Worst CTCAE grade of biochemical parameters by patient [Safety set]	12_2_2_4_2a.RTF
12.2.2.4	Worst CTCAE grade of biochemical parameters by cycle [Safety set]	12_2_2_4_2b.RTF
12.2.2.4	Shift table of Worst CTCAE grade by patient according to grade at baseline for biochemical parameters [Safety set]	12_2_2_4_2c.RTF
12.2.2.4	Worst value of creatinine clearance by patient according to value at baseline [Safety set]	12_2_2_4_2d.RTF
12.2.2.4	Worst CTCAE grade of SGOT/AST by patient according to the presence of liver metastases at baseline [Safety set]	12_2_2_4_2e.RTF
12.2.2.4	Worst CTCAE grade of SGPT/ALT by patient according to the presence of liver metastases at baseline [Safety set]	12_2_2_4_2f.RTF
12.2.2.4	Worst CTCAE grade of bilirubin by patient according to the presence of liver metastases at baseline [Safety set]	12_2_2_4_2g.RTF
12.2.2.4	Worst CTCAE grade of alkaline phosphatase by patient according to the presence of liver and/or bone metastases at baseline [Safety set]	12_2_2_4_2h.RTF
12.2.2.4	Listing of LBH values >500 IU/L [Safety Set]	12_2_2_4_2i.RTF
12.3.1.1	Summary of deaths [Safety set]	12_3_1_1a.RTF
12.3.1.1	Listing of dead patients within 30 days after last administration or more than 30 days after last administration, reason of death, relationship to treatment [Safety set]	12_3_1_1b.RTF
12.3.1.2	Listing of Serious Adverse Events [Safety set]	12_3_1_2.RTF
14.1.1	Prior medications whatever the indication per patient at baseline [ITT]	14_1_1.RTF
14.1.2	Prior medications with a tumour related indication per patient at baseline [ITT]	14_1_2.RTF
14.1.3	Prior medications with a prophylactic indication per patient at baseline [ITT]	14_1_3.RTF
14.1.4	Prior medications with pre-treatment event indication per patient at baseline [ITT]	14_1_4.RTF
14.1.5	Prior medications with medical history indication per patient at baseline [ITT]	14_1_5.RTF
14.1.6	Prior medical history by patient according to MedDRA System Organ Class and Preferred Term [ITT]	14_1_6.RTF
14.1.7	Pre-treatment events by patient according to MedDRA System Organ Class and Preferred Term [ITT]	14_1_7.RTF
14.3.1a	Concomitant medications whatever the indication per patient [ITT]	14_3_1a.RTF
14.3.1b	Concomitant medications whatever the indication per cycle [ITT]	14_3_1b.RTF
14.3.2a	Concomitant medications with a tumour related indication per patient [ITT]	14_3_2a.RTF
14.3.2b	Concomitant medications with a tumour related indication per cycle [ITT]	14_3_2b.RTF
14.3.3a	Concomitant medications with a prophylactic indication per patient [ITT]	14_3_3a.RTF
14.3.3b	Concomitant medications with a prophylactic indication per cycle [ITT]	14_3_3b.RTF
14.3.4a	Concomitant medications with pre-treatment event indication per patient [ITT]	14_3_4a.RTF
14.3.4b	Concomitant medications with pre-treatment event indication per cycle [ITT]	14_3_4b.RTF
14.3.5a	Concomitant medications with medical history indication per patient [ITT]	14_3_5a.RTF
14.3.5b	Concomitant medications with medical history indication per cycle [ITT]	14_3_5b.RTF
16.2.1	Discontinued patients	16_2_1_1.RTF
16.2.1	Follow-Up data	16_2_1_2.RTF
16.2.3	Analysis sets	16_2_3_1.RTF
16.2.3	Eligibility criteria	16_2_3_2.RTF
16.2.3	Randomization criteria	16_2_3_3.RTF
16.2.4	Patients' characteristics	16_2_4_1.RTF
16.2.4	Disease characteristics	16_2_4_2.RTF
16.2.4	Prior surgery for breast carcinoma	16_2_4_3a.RTF

SECTION	Title	RTF reference
16.2.4	Prior radiotherapy for breast carcinoma	16_2_4_3b.RTF
16.2.4	Prior chemotherapy for breast carcinoma	16_2_4_3c.RTF
16.2.4	Prior treatment for breast carcinoma (Prior Hormonal Treatment or Castration)	16_2_4_3d.RTF
16.2.4	Medical and Surgical History, Concomitant disease	16_2_4_4.RTF
16.2.4	Pre-treatment events	16_2_4_5.RTF
16.2.4	Blood and Platelet transfusion	16_2_4_6.RTF
16.2.5	Treatment administration per cycle	16_2_5_1.RTF
16.2.5	Treatment administration of Vinflunine	16_2_5_2.RTF
16.2.5	Treatment administration of Capecitabine	16_2_5_3.RTF
16.2.5	Cumulative dose, dose intensity and relative dose intensity per arm and per cycle	16_2_5_4.RTF
16.2.5	Treatment modifications	16_2_5_5.RTF
16.2.6	Tumour assessments	16_2_6_1.RTF
16.2.6	Work-Up	16_2_6_2.RTF
16.2.6	Efficacy parameters (PFS)	16_2_6_3.RTF
16.2.7	Adverse Events by patient (Reported Term, Preferred Term and Dates)	16_2_7_1.RTF
16.2.7	Adverse Events by System Organ Class and Preferred Term	16_2_7_2.RTF
16.2.7	Drug-related Adverse Events by patient (Reported Term, Preferred Term and Dates)	16_2_7_3.RTF
16.2.7	Drug-related Adverse Events by System Organ Class and Preferred Term	16_2_7_4.RTF
16.2.7	Serious Adverse Events by patient (Reported Term, Preferred Term and Dates)	16_2_7_5.RTF
16.2.7	Serious Adverse Events by System Organ Class and Preferred Term	16_2_7_6.RTF
16.2.7	Patient deaths	16_2_7_7.RTF
16.2.8	Individual haematological laboratory measurements by patient - grades and values	16_2_8_1.RTF
16.2.8	Individual biochemical laboratory measurements by patient - grades and values	16_2_8_2.RTF
16.2.8	Blood products	16_2_8_3.RTF
16.2.8	Pregnancy test results	16_2_8_4.RTF
16.2.8	Tumour Markers	16_2_8_5.RTF
16.2.9	Temperature, vital signs, weight	16_2_9_1.RTF
16.2.9	Neurological examination, physical examination	16_2_9_2.RTF
16.2.9	ECG results	16_2_9_3.RTF
16.2.10	Prior and Concomitant medications	16_2_10_1.RTF
16.2.10	Concomitant Radiotherapy	16_2_10_2.RTF
16.2.10	Concomitant surgery	16_2_10_3.RTF

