### **7.1. INTENT-TO-TREAT POPULATION**

All randomised patients will be included in the intent-to-treat population. They will be analysed in the arm they were assigned by randomisation.

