### **7.4. EVALUABLE POPULATION FOR SAFETY**

All treated patients will be included in the safety analysis. They will be analysed in the treatment arm they actually received.

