## **8. STATISTICAL METHODS**

### **8.1. STATISTICAL SOFTWARE AND METHODOLOGY**

Most analyses will be carried out with 9.3 version of SAS® for Windows® (or later version if available). All statistical tests will be two-sided at a 5% level of significance unless specified otherwise.

All baseline descriptive statistics will be presented in summary tables by treatment arm and overall.

Continuous data will be summarized with the following items: frequency, median (if  $n \geq 3$ ), min, max, mean and standard deviation if relevant.

Categorical data will be presented in contingency tables with frequencies and percentages of each modality (including missing data modality).

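### Exposure and dose-change tables are set on ITT by randomised arm while toxicity tables use treated patients by arm received, so the two may describe different patients

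*SAP*

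**What the plan says.** In SAP Appendix 1 every output numbered 12.1 carries the ITT tag. Examples are "Summary of exposure [ITT", "Exposure: Cumulative dose, actual dose intensity and relative dose intensity by patient [ITT" and "Dose reduction of Vinflunine and reasons [ITT". SAP 7.1 defines that set: "All randomised patients will be included in the intent-to-treat population", each in her randomised arm. SAP 9.2, which specifies these outputs, names no other population.

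The tags agree with the opening of SAP section 7, which says that every analysis uses ITT and that no other population will be formed. The same SAP then defines a second population in 7.4, made up of treated patients: "They will be analysed in the treatment arm they actually received". Section 11 uses that population for all safety analyses, and Appendix 1 follows it, as in "Summary of Adverse Events [Safety set". The protocol synopsis (Statistical methods) also puts descriptive analyses on ITT but gives the safety analysis its own evaluable population.

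Three further rules matter:

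- SAP 8.1 presents categorical data as "frequencies and percentages of each modality (including missing data modality".
- SAP 9.2.2 fixes the planned dose intensity (PDI) by arm: "Tables 9-3 and 9-4 give for each treatment arm of the study the PDI".
- SAP Table 9-2 gives each arm its own capecitabine dose bands.

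**The concern.** Exposure is the background against which toxicity is read, so both should cover the same patients, grouped in the same way. As tagged, they need not.

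- **A randomised patient who was never dosed** is in the exposure tables but not in the adverse-event tables. She cannot have a dose reduced, delayed or cancelled, so counting her in the denominator lowers those patient-level percentages.
- **A patient who received the other arm's regimen** has her exposure shown in the assigned arm and her adverse events in the arm received. Her relative dose intensity (RDI) is then divided by a plan that did not govern her treatment.

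At stake is the accuracy of the exposure description. The PFS summary is not touched, because ITT is the right set for it.

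**Working it through.** **1. Count of outputs.** The 12.1 rows of Appendix 1 are: exposure summary (1), route and setting (2), cycles (1), dose intensity by patient and by cycle (2), delay (1), vinflunine reduction (2), capecitabine reduction (2), capecitabine cancellation (1), infusion interruption (1). That makes 13, all tagged ITT.

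**2. The plan's own PDI figures.** PDI = planned dose per cycle / 3 weeks (SAP 9.2.2).

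- Arm A vinflunine: 280 / 3 = 93.33 mg/m²/wk
- Arm A capecitabine: 825 × 2 × 14 / 3 = 23100 / 3 = 7700
- Arm B capecitabine: 1250 × 2 × 14 / 3 = 35000 / 3 = 11666.67

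All three agree with Tables 9-3 and 9-4.

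**3. Never-dosed patients.** There are 112 randomised patients at 1:1, so about N = 56 per arm; the actual split is not given. Let u be the number never dosed in an arm and k the number with at least one dose change. The rate among treated patients is k / (N − u) and on ITT it is k / N, so the ITT rate is the treated rate × (N − u) / N. Both u and k = 28 are assumptions for illustration.

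| u | Treated | ITT | Difference (points) |
|---|---|---|---|
| 0 | 28/56 = 50.0% | 50.0% | 0 |
| 1 | 28/55 = 50.9% | 50.0% | 0.9 |
| 3 | 28/53 = 52.8% | 50.0% | 2.8 |

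The relative loss is u / N: 1/56 = 1.8% and 3/56 = 5.4%. A treated rate of 40% would show as 39.3% (u = 1) or 37.9% (u = 3).

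This applies only to patient-level percentages. A never-dosed patient has no cycles, so she adds nothing to per-cycle rates. Her dose intensity is undefined (SAP 9.2.3 sums over cycles given), so she drops out of the medians.

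**4. Capecitabine RDI after receiving the other regimen at full dose.**

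- Randomised to A, given B: 11666.67 / 7700 = 151.5%, in the class above 100%
- Randomised to B, given A: 7700 / 11666.67 = 66.0%, in the class of 90% or less

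Against the regimen received, both are 100%. The distortion can also hide under-dosing: a patient randomised to A and given 75% of the arm B plan would show 0.75 × 151.5% = 113.6%.

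**5. Table 9-2 dose categories.** A patient randomised to B who takes 825 mg/m² falls in arm B's band from 787.5 to 1100 and is labelled 950. In the other direction, 1250 mg/m² falls in arm A's own 1250 band. At full dose, the category is therefore wrong in one direction only.

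**6. Vinflunine given to a patient randomised to B.** Table 9-4 has no vinflunine PDI, so her vinflunine RDI cannot be formed. The vinflunine reduction, interruption and route outputs (9.2.5.1, 9.2.7, 9.2.9) are specified for arm A only, so on ITT she would be missing from them.

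**The case against.** The case for leaving the tags alone has real force.

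- **The tags follow a stated rule.** Section 7 orders ITT for everything, and exposure sits in SAP section 9 (treatment group description), not in the safety section. This stands: the source of the problem is the conflict between section 7 and sections 7.4 and 11. Correcting that sentence alone would still leave the 13 tags as they are.
- **Denominators are not stated.** An all-ITT denominator is the natural reading of the tag and of the missing-category rule, but it is an inference. A separate missing row would let a reader remove undosed patients. The patient-level shell in 9.2.9 has no such row and does not define its patient total. So dilution is possible, not established.
- **Cross-treatment may never occur.** Section 7.4 is an allocation rule and does not report or predict such a case. The trial is open-label and only one arm has an intravenous drug. This stands too.
- **The adverse-event and dose-change tables count different things.** Section 11.2.1 counts events requiring interruption or adjustment; the 12.1 tables count changes for any reason. Their rates would differ even on one population, so a difference between them would not by itself show a population error. The mismatch in patients and arms remains.
- **Readers can recover the figures.** Randomised and treated counts are tabulated by arm, and individual administration and dose-intensity listings are planned (16.2.5). This limits the harm, but leaves readers to recompute the tables.

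A reader might infer that all 13 tables are diluted and scored against the wrong planned dose. The documents do not support that. The planned-dose effect reaches only the two dose-intensity tables and the outputs that use the Table 9-2 categories. Dilution reaches only patient-level percentages.

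**Conclusion.** The point holds as a minor, conditional inconsistency. Under the SAP's own definitions, exposure and toxicity would be described on different sets and with different arm assignment whenever a randomised patient was undosed or received the other regimen.

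For 1 to 3 undosed patients of about 56 per arm, the effect on a patient-level rate near 50% is about 1 to 3 percentage points, assuming that undosed patients stay in the denominator. For each patient given the other regimen at full dose, it is one capecitabine RDI of 151.5% or 66.0% in place of 100%, in the wrong RDI class. The documents give no number of undosed or cross-treated patients. If there were none, nothing changes.

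**What to change.** 1. **SAP section 7:** replace the blanket rule with one that assigns ITT to disposition, baseline and PFS, and the section 7.4 population to exposure and safety. Without this, retagging would widen the contradiction.
2. **Appendix 1, section 12.1:** retag the 13 outputs as [Safety set]. Identify them by title, because the file names 12_1_2.RTF and 12_1_3.RTF are each given to two tables; correct those at the same time.
3. **Appendix 1, tables 14.3.1a to 14.3.5b:** retag these ten on-study concomitant-medication tables in the same way. They fall under 9.2.10 and describe medication given alongside study treatment, so the same reasoning applies.
4. **SAP 9.2:** add a sentence that exposure, dose intensity and dose modifications are described in treated patients by treatment received, using the planned dose intensity and dose categories that the SAP already sets for that treatment.

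The cost is 13 + 10 = 23 table labels, two text edits, and the matching population and arm variables in the programs. No new data are needed.
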